3.0 PATIENT SELECTION

3.1 Inclusion Criteria

1. Patients 18 and older.
2. Patients willing and able to sign consent.
3. Patients with an organ confined renal mass planning to undergo a robotic assisted partial nephrectomy (RAPN).
4. Patient with Karnofsky Performance Status (KPS) equal to or greater than 40.

3.2 Exclusion Criteria

1. Patients under 18.
2. Patients with Karnofsky Performance Status (KPS) less than 40.
3. Patients with non-organ confined renal masses (invading renal vein, inferior vena cava, peri-renal tissue, ipsilateral adrenal gland, or metastasis).
4. Patients with bilateral synchronous renal masses.
5. Patients who can not discontinue, Plavix, Coumadin or other anti-platelet or anti-coagulant medications.
6. Patients with renal lesions determined to be too complex to perform a RAPN without clamp by the surgeon. (The renal mass may be deemed too difficult based on pre-operatively radiological findings. The surgeon's decision to exclude a mass from a robotic assisted partial nephrectomy would be based on a higher risk of positive margin or complication if a RAPN was performed.)

3.3 Inclusion of Women and Minorities

Both men and women and members of all races and ethnic groups are eligible for this trial.

4.0 REGISTRATION PROCEDURES

Patients must not start any protocol intervention prior to registration through the Siteman Cancer Center.

The following steps must be taken before registering patients to this study:

1. Confirmation of patient eligibility
2. Registration of patient in the Siteman Cancer Center database
3. Assignment of unique patient number (UPN)

4.1 Confirmation of Patient Eligibility

The following information is required to confirm patient eligibility prior to registering patient:

1. Registering MD's name
2. Patient's race, sex, and DOB
3. Three letters (or two letters and a dash) for the patient's initials
4. Copy of signed consent form
5. Planned date of enrollment
6. Completed eligibility checklist, signed and dated by a member of the study team
7. Copy of appropriate source documentation confirming patient eligibility

4.2 Patient Registration in the Siteman Cancer Center Database

All patients must be registered through the Siteman Cancer Center database (SCCdb).

4.3 Assignment of UPN

For the purpose of this study, each patient will be identified with a unique patient number (UPN) which will be assigned consecutively at the time of registration in the SCCdb. All data will be recorded with this identification number on the appropriate CRFs. The UPN will not include the patient's initials as this is considered identifiable information per Siteman Cancer Center Guidelines.

5.0 TREATMENT PLAN

5.1 Preoperative Evaluation

Patients will be evaluated to determine whether they meet the criteria specified in Section 3.1. Patients meeting these criteria will continue to next step.

Patients will have standard of care blood work which will include serum creatinine, preoperatively. Tumor characteristics based on preoperative cross-sectional imaging will be recorded, particularly components of the nephrometry score.

5.2 Operative Procedure

5.2.1. Randomization

Randomization will take place in the operating room, after feasibility of RAPN off clamp is confirmed. Patients will be randomized to either off-clamp RAPN or traditional clamped RAPN in a 1:1 ratio, for a total of 40 patients allocated to each group. To minimize selection bias, a randomization table will be developed before initiation of enrollment.

Envelopes containing randomization assignments will be created, sequentially numbered and sealed. Once enrollment is initiated, randomization envelopes will be opened for each subject after informed consent is granted and study eligibility is confirmed in the operating room.

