Open NSS traditionally involves clamping of the renal hilar vessels and an abundant use of ice to ensure tissue hypothermia. However, techniques of achieving kidney hypothermia have not been translated to minimally invasive NSS. Thus, renal hilar clamping during minimally invasive NSS is performed under warm ischemia. Increased duration of warm ischemia time (WIT) has been demonstrated to negatively impact short and long-term renal function [18]. As a result, many techniques for limiting WIT have been described, including segmental renal artery clamping, renal parenchymal clamping, early unclamping, and unclamped NSS following administration of hypotensive agents [19-22].

Several years ago, the Principal Investigator developed a technique where RAPN is performed without clamping of the renal hilar vessels and without systemic blood pressure manipulation. This technique is applicable to all renal tumors that are appropriate for partial nephrectomy.

In order to determine the efficacy of this procedure, a retrospective chart review, matched cohort study was performed at Washington University comparing 29 patients who underwent off-clamp RAPN for suspected renal cell carcinoma with a matched 29 patients that underwent RAPN with hilar clamping. The procedures were performed from 3/2008 to 9/2011, and the patients in each group were similar in nephrometry score and baseline renal function. The off-clamp patients experienced an estimated blood loss of 146.4cc, while the hilar clamped RAPN group had an estimated blood loss of 103.9cc ($p=0.039$). The complications were similar in the two groups with no complications seen in the off-clamp group and only one Clavien-2 complication in the hilar clamp group. The mean eGFR decline was 4.9 ml/min/1.73m² in the off-clamp group and 11.7ml/min/1.73m² in the hilar clamp group ($p=0.033$). In summary, the off-clamp RAPN patients experienced less decline in renal function while experiencing similar morbidity [23].

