9.2 Study Design

This is a single institution, prospective, randomized, controlled study to evaluate the off-clamp RAPN technique. Parallel group design with randomization allocation ratio of 1:1 to off-clamp RAPN technique (study treatment) and traditional clamped RAPN technique (control) will be utilized. Study will be conducted at Washington University and will enroll approximately 80 participants over the course of the study.

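### Nephrometry score is recorded before surgery but is named neither as a stratification factor nor as a covariate, so the arm comparison gives up some precision that would cost nothing to recover

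*Combined protocol and SAP*

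**What the plan says.** Section 5.1 provides that "Tumor characteristics based on preoperative cross-sectional imaging will be recorded, particularly components of the nephrometry score". The score is therefore available before allocation, because under section 5.2.1 "Randomization will take place in the operating room, after feasibility of RAPN off clamp is confirmed".

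On the allocation itself, section 5.2.1 says that "To minimize selection bias, a randomization table will be developed before initiation of enrollment". It describes sequentially numbered sealed envelopes and allocation "in a 1:1 ratio, for a total of 40 patients allocated to each group". Section 9.2 repeats the 1:1 ratio and says the study "will enroll approximately 80 participants over the course of the study". Neither section mentions strata, blocks or minimization factors.

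Section 9.3 calls the analysis descriptive. It plans summaries of demographic and clinical characteristics, recurrence and complications, and Kaplan-Meier estimates. It names no between-arm comparison of eGFR or split renal function (SRF), and no covariate.

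Tumour complexity appears in two other places. Section 1.1 says of the retrospective matched cohort that "the patients in each group were similar in nephrometry score and baseline renal function". Section 3.2, exclusion 6, removes "Patients with renal lesions determined to be too complex to perform a RAPN without clamp by the surgeon" and explains that such a decision "would be based on a higher risk of positive margin or complication if a RAPN was performed".

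**The concern.** The investigators treat complexity as relevant. They report that it was similar between the pilot groups, collect it on every patient, and link it to margins and complications, both of which are secondary outcomes. The plan for the randomized comparison then makes no stated use of it.

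In a trial of 80, a baseline factor that predicts the outcome adds scatter to the estimated arm difference, and the arms can differ on it by chance. If no adjustment is specified in advance, that scatter stays in the estimate. Any adjustment made after an imbalance has been seen would be open to the charge that it was chosen to suit the result. At stake are some precision on the primary outcome and the credibility of a single-institution result.

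**Working it through.** The plan gives no alpha, power, target effect or SD for 40 per group, so that figure cannot be reproduced. The check therefore concerns how likely an imbalance is, what it would do, and what adjustment would recover.

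**Inputs from the documents.** 40 per arm (5.2.1). Pilot eGFR decline 11.7 and 4.9 ml/min/1.73m², difference 11.7 − 4.9 = 6.8, p = 0.033, 29 against 29 patients (1.1).

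**Assumptions.** 30-50% of randomized patients have a higher score, and such patients lose 5-10 ml/min/1.73m² more eGFR. The documents give neither figure.

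1. *Imbalance, continuous score.* The standardized difference between arms has SD √(2/40) = 0.224. P(|difference| > 0.25 SD) = 2[1 − Φ(0.25/0.224)] = 26%. Above 0.4 SD it is 7.4%, and above 0.5 SD it is 2.5%.

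2. *Imbalance, binary split.* With K higher-score patients among 80 and an unstratified 40:40 list, the number in one arm is hypergeometric (80, K, 40).

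| Higher-score share | K | P(arms differ by ≥6 patients, 15 points) | P(≥8 patients, 20 points) |
|---|---|---|---|
| 20% | 16 | 16% | 4.8% |
| 30% | 24 | 22% | 8.7% |
| 40% | 32 | 25% | 11.0% |
| 50% | 40 | 26% | 11.7% |

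3. *SD of eGFR change, back-calculated (assumption).* Treating the pilot p-value as a two-sample t test on 56 df, t = 2.186, so SE = 6.8/2.186 = 3.11 and SD = 3.11/√(2/29) = 11.84. Paired-t and z versions give 11.5 and 12.1.

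4. *What an imbalance does.* A 15-point imbalance shifts the eGFR difference by 0.15 × 5 = 0.75 to 0.15 × 10 = 1.5. The SE of the difference with 40 per arm is 11.84 × 0.224 = 2.65, so the shift is 0.75/2.65 = 0.28 to 1.5/2.65 = 0.57 of one SE.

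5. *What adjustment recovers.* Variance explained by a binary factor with share p and effect d is p(1 − p)d²/SD², with SD² = 140.3. The equivalent sample size is 80/(1 − R²).

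| Effect d | Share p | R² | 80 patients are worth |
|---|---|---|---|
| 5 | 0.3 | 5.25/140.3 = 3.7% | 83.1 |
| 5 | 0.5 | 6.25/140.3 = 4.5% | 83.7 |
| 10 | 0.3 | 21/140.3 = 15.0% | 94.1 |
| 10 | 0.5 | 25/140.3 = 17.8% | 97.3 |

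6. *In terms of power.* For a difference of 6.8 at two-sided 5%, power is 72.8% unadjusted. It becomes 73.3%, 74.6%, 76.8%, 80.0% and 84.2% if the score correlates with eGFR change at 0.1, 0.2, 0.3, 0.4 and 0.5. Correlations of 0.2 and 0.4 correspond to R² of 4% and 16%, close to the range in step 5.

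Steps 5 and 6 credit the score alone. If baseline eGFR carries part of the same information, the score adds less once the baseline value is in the model.

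**The case against.** Unstratified 1:1 randomization is valid. It leaves the comparison unbiased, and a correct unadjusted standard error already allows for chance imbalance. That stands in full. A reader might infer that an imbalance would distort every outcome, but step 4 puts a 15-point imbalance well inside ordinary sampling error. The documents link complexity only to margins and complications. They give no figure tying the score to eGFR, SRF, blood loss or operative time, and nothing ranks it as the strongest prognostic factor.

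A reader might also infer from the pilot that the trial must balance on the score. That does not follow: a retrospective matched cohort needs similar groups because nothing was randomized.

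Eligibility weakens the concern further. Exclusion 6 and the feasibility check in the operating room remove the most complex masses, so the remaining spread is narrower by an amount that is not stated.

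Section 5.2.1 is silent on stratification and does not rule it out; its sentence about the table is not wrong in itself. Section 9.3 could show the score among the clinical characteristics, although a baseline table adjusts nothing.

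Finally, the larger gap is that 9.3 specifies no between-arm analysis of the primary outcome. That is true, and it is why the remedy has to begin by writing that comparison. It does not remove the case for naming the covariates at the same time.

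**Conclusion.** The point holds as one of precision and pre-specification, not of bias. A measured baseline factor is left out of both the stated allocation and the stated analysis. With 40 per arm, the chance of a moderate imbalance on it is about one in four (26% for more than 0.25 SD; 22-26% for at least 15 points at an assumed 30-50% share).

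The gain from adjusting runs from small to useful. An added eGFR loss of 5 in higher-score tumours explains about 4% of the variance and makes 80 patients worth about 83. An added loss of 10, which exceeds the whole pilot difference of 6.8, explains 15-18% and makes them worth about 94-97. These figures rest on the assumed share and effect, on the pilot-derived SD, and on all 80 patients having the outcome. The conclusion that the envelopes must be stratified is not supported.

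**What to change.** In section 9.3, pre-specify the between-arm comparison of eGFR change and of SRF change as a linear model (ANCOVA) with arm, the baseline value of that outcome and nephrometry score as covariates. Include nephrometry score as a covariate in the comparisons of blood loss and operative time. State this before outcome data by arm are examined.

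All the variables are already collected, so the change needs a short paragraph in 9.3 and no new data, visits or patients. If the score proves weakly prognostic, the loss is one degree of freedom per model.

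If the randomization list has not been issued, stratifying the envelopes by a pre-set nephrometry cut is an option. It would need a second envelope set with permuted blocks of varying size, and the stratum in the model. The final split might then be 41:39 or 42:38 rather than exactly 40:40. If the list has been issued, leave it unchanged; the covariates alone are sufficient.

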5.2.2. Day of surgery

Standard preoperative and perioperative procedures for RAPN will be followed in both groups. For the control group (traditional clamped technique), RAPN will be performed in the standard fashion. For the treatment group (off-clamp technique), RAPN will be performed with our off-clamp technique. There is also a possible chance the procedure may be switched intraoperatively due to a variety of factors. For example, intraoperatively a patient undergoing a RAPN off-clamp may require emergent conversion to a traditional hilar clamped RAPN for excessive bleeding. Also, a patient undergoing either RAPN off-clamp or traditional hilar clamped RAPN could require conversion to either open partial nephrectomy, open radical nephrectomy, or laparoscopic radical nephrectomy given intraoperative conditions. A change in technique would only take place if required to maintain patient safety.

5.2.3. Description of the off-clamp RAPN technique

In the off-clamp RAPN technique, after surgical access is gained, kidney is mobilized and Gerota's fascia is incised. The perinephric fat is dissected away from the renal capsule to expose the tumor.

Intravenous mannitol (12.5 grams) is administered by anesthesia. Two robotic bulldog clamps are introduced to allow for expeditious clamping of the hilum if necessary. The margins of the mass are outlined circumferentially with monopolar electrocautery on the robotic scissors. This cautery is continued until an appropriate plane of dissection is found. Forceps are used to bluntly separate the tumor from the residual renal parenchyma with intervening tissue cauterized meticulously with the monopolar scissors. If a large vessel from the renal parenchyma is noted to be bleeding during tumor excision, the robotic bulldogs can be applied to the vessel in the resection bed. This controls the bleeding vessel(s) until suture ligation or clip application of the vessel(s) can be performed. Additionally, larger vessels that are directly supplying the tumor can be controlled with clips if hemostasis with cautery is not adequate. Mobilization of the tumor is continued circumferentially until complete excision of the tumor is achieved. The bedside assistant uses suction and applies countertraction as necessary during tumor excision. The specimen is then placed above the liver or spleen for later retrieval.

The base of the resection bed is cauterized. The insufflation pressure of the [name]
Off Clamp Randomization v6

pneumoperitoneum is decreased and the resection bed is examined for any ongoing bleeding.

Any patent venous sinuses or arteries at the base of the resection are oversewn. If the collecting system has been entered, it is similarly closed. The defect in the renal parenchyma is closed using a sliding clip renorrhaphy technique. Gerota's fascia is then similarly reapproximated.

The specimen is entrapped in a specimen bag and then the robot is undocked. The specimen is removed through a port site with extension of the incision as necessary.

The fascia for the ports is closed and skin is reapproximated.

5.3 Risks of RAPN

There are multiple potential risks associated with a RAPN. Complications include but are not limited to the following: hemorrhage requiring transfusion, urinary leak/fistula, abscess, loss of renal function, injury to surrounding organs, conversion to an open surgery, conversion to a radical nephrectomy, incisional hernia, deep venous thrombosis, pulmonary embolism, myocardial infarction, stroke, and death.

A recent multi-institutional study reported complication rates for 450 RAPN procedures. The overall complication rate was 15.8% with 76.1% Clavien grade I-II and 23.9% Clavien grade III-IV. Hemorrhage requiring a transfusion occurred in 5.1% and arterial embolization to stop hemorrhage in 0.4%. A urine leak occurred in 1.6% with no patient requiring explorative operations for urinary leak. Intra-operative conversion to radical nephrectomy occurred in 1.6%. No deaths occurred in the 450 cases.

5.4 Postoperative Care

The postoperative management is standard of care for all patients who undergo RAPN.

Three month post op visit:

- CR/eGFR
- Renal Scan
- CT/MRI of abdomen
- Chest x-ray (CXR)

5.5 Duration of Follow-Up

The follow up management is standard of care but uniquely different for patients based on pathologic outcome. Patients with a malignant (cancerous) surgical pathology will be followed for a period of 3 years. Patients with a benign (non-cancerous) surgical pathology will only be followed through a period of 3 months postoperatively. Patients removed from

this study for unacceptable adverse events will be followed until resolution or stabilization of the adverse event.

Yearly follow up visits:

- CR/eGFR
- CT/MRI of abdomen
- Chest x-ray (CXR)

5.6 Criteria for Removal from Study

If at any time the constraints of this protocol are considered to be detrimental to the patient's health and/or the patient no longer wishes to proceed with the protocol intervention, the patient should be removed from the study and the reason(s) for discontinuation documented in the case report forms.

Otherwise, the patient will receive the intervention and be followed as described.

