2.0 OBJECTIVES

2.1 Primary Objective

1. To determine if off-clamp RAPN technique better preserves long-term renal function than the traditional clamped RAPN technique.

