9.0 STATISTICAL CONSIDERATIONS

9.1 Study Objectives and Endpoints

Primary Outcome:

Evaluation of renal function following RAPN with or without hilar clamping using:

1. Decline in estimated glomerular filtration rate (eGFR). eGFR is calculated from serum creatinine using the Chronic Kidney Disease Epidemiology Collaboration formula [11]. Decline in eGFR = Postoperative eGFR – Preoperative eGFR.
2. Decline in split renal function (SRF). SRF is a percentage of the total renal function supplied by one kidney. Ideally each kidney has a SRF of 50%. SRF is measured during renal scintigraphy (renal scan). Decline is SRF =preoperative SRF- postoperative SRF (3 month).

Secondary Outcomes:

1. Oncological outcomes:
 - a. Pathological results
 1. Pathologic margin status
 2. Tumor histology, including Fuhrman grade if applicable
 3. Distance between tumor margin and surgical margin

- b. Evidence of disease recurrence or metastasis on follow-up imaging
 - 1. Recurrence free survival
- 2. Perioperative outcomes
 - a. Estimated blood loss
 - b. Operative time and warm ischemia time
 - c. Intra-operative complications, including but not limited to injury to the surrounding organs and vessels, excessive blood loss requiring blood transfusions, and conversion to radical nephrectomy or open surgery.
 - d. Length of postoperative hospital stay
 - e. Postoperative complications, including but not limited to urine leak, urinoma, abscess, pseudoaneurysm, ileus, blood transfusion requirements, incisional hernias, wound infection, blood transfusion requirements, deep venous thrombosis, pulmonary embolism, myocardial infarction, stroke, and death.

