APPENDIX C: Study Schedule of Events

	Pre-Operative Assessments	Surgery	Post-Operative Assessments		
	Baseline ¹	RAPN	1 day Post RAPN	3 months Post RAPN	Every 12 months ²
Informed Consent	X				
Demographics	X				
Medical & Surgical History	X				
Height & Weight	X				
Serum Creatinine/eGFR	X		X	X	X
Renal Scan	X ¹			X	
CT/MRI of abdomen	X ¹			X	X
CXR	X ¹			X	X
Incl./Excl. Criteria Confirmation	X				
Randomization		X			
Perioperative Outcomes		X			
Pathology results		X			
Adverse Event Assessment				X	
Assessment of Evidence of Disease Recurrence				X	X

¹ Scans (Renal Scan, CT/MRI of abdomen and Chest Xray (CXR)) performed prior to or at time of baseline assessments per standard of care

² From the date of 3-mo follow up for total of 3 years only for patients with malignant pathological outcome

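### Section 5.6 ends study participation, not only the intervention, so a randomised patient removed after surgery and before month 3 would contribute no postoperative split renal function value

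*Combined protocol and SAP*

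**What the plan says.** Section 5.6 (Criteria for Removal from Study) has two triggers and no time limit. One is that the protocol's constraints are considered harmful to the patient's health. The other is that "the patient no longer wishes to proceed with the protocol intervention". In either case "the patient should be removed from the study and the reason(s) for discontinuation documented in the case report forms". The section then closes with "Otherwise, the patient will receive the intervention and be followed as described".

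Section 5.5 (Duration of Follow-Up) has the only text on follow-up after removal. Patients removed from "this study for unacceptable adverse events will be followed until resolution or stabilization of the adverse event". It names no creatinine, eGFR or renal scan for them.

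The primary objective in section 2.1 is "To determine if off-clamp RAPN technique better preserves long-term renal function than the traditional clamped RAPN technique". Section 9.1 lists two primary measures. The SRF measure is tied to one visit: "Decline is SRF =preoperative SRF- postoperative SRF (3 month". The eGFR measure names no postoperative time point.

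Section 5.4 describes care after surgery as standard for patients who have a robot-assisted partial nephrectomy (RAPN). It lists creatinine/eGFR and a renal scan at 3 months.

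**The concern.** Stopping an intervention and leaving a study are different events, and section 5.6 treats them as one. Its patient-choice trigger concerns the intervention only. A patient can decline that and still be willing to have a 3-month result recorded, yet the rule takes the patient out of the study.

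The stake is primary-outcome data on randomised patients. Someone removed because the protocol was judged harmful, or because of an adverse event, may have a different renal outcome from someone who stays. Such a loss could be related to outcome, and it could differ between arms. A result that was never recorded cannot be recovered at the analysis stage.

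**Working it through.** This is mainly a check of text. The steps are as follows.

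**1. Who is followed after removal.** The closing sentence of 5.6 limits scheduled follow-up to patients who are not removed. Section 5.5 adds follow-up for one group of removed patients, those with unacceptable adverse events, and ends it when the event resolves or stabilises. No section extends the 3-month renal measurements to a removed patient.

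**2. When the primary measures are taken** (sections 5.4 and 5.5, Appendix C).

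| Measure | Baseline | Day 1 | Month 3 | Yearly |
|---|---|---|---|---|
| Creatinine/eGFR | yes | yes | yes | malignant pathology only |
| Renal scan (SRF) | yes | no | yes | no |

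The list under "Yearly follow up visits" in 5.5 contains no renal scan. The Appendix C footnote restricts the annual column: "From the date of 3-mo follow up for total of 3 years only for patients with malignant pathological outcome".

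**3. What is lost if removal falls between surgery and month 3.**
- SRF: the only postoperative value. No later scan can replace it.
- eGFR: the month 3 value and any yearly values. The day 1 value may already be on file.
- For benign pathology, month 3 is the last scheduled measurement of any kind.

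**4. Size per patient.** Section 5.2.1 gives 40 patients per group. Two groups make 40 + 40 = 80, which agrees with section 9.2. One patient without SRF is 1/40 = 0.025 = 2.5% of an arm.

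**5. Why no bias figure follows.** Suppose k of 40 patients in an arm are removed, and their mean decline differs from that of the remaining patients by D. Leaving them out shifts that arm's mean by (k/40) × D. The documents give neither k nor D, and no SRF values at all.

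For scale only, in eGFR units, borrow the gap between groups in the retrospective cohort of section 1.1: D = 11.7 − 4.9 = 6.8 ml/min/1.73m². Both this D and the values of k below are assumptions.
- k = 2: (2/40) × 6.8 = 0.34
- k = 4: (4/40) × 6.8 = 0.68
- k = 8: (8/40) × 6.8 = 1.36

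If the removed patients were off-clamp and did worse, the shift would favour off-clamp. If they were in the clamped arm and did worse, or were off-clamp and did better, it would go the other way.

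**The case against.** The strongest objection is that the rule can reach very few randomised patients. Section 5.2.1 places randomisation in the operating room, after feasibility of the off-clamp operation is confirmed, and the intervention is a single operation. A patient who changes their mind will nearly always do so before that point, at no cost in randomised data. Later management is standard of care, so few protocol constraints remain that could be judged harmful. This stands, and it limits the size of the problem. It does not remove it: 5.6 has no time limit, and 5.5 expects some removals for adverse events, although 5.6 does not name adverse events as a trigger.

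A second objection is that the data are already provided for. Section 5.4 makes the 3-month tests routine, section 7.0 schedules a follow-up form at 3 months without stating an exception, and section 6.2 assesses complications up to that visit. This stands in part, because results may well exist. None of these sections mentions removed patients, however, and 5.6 addresses them directly by restricting scheduled follow-up to the others.

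Third, the eGFR loss is less certain than the SRF loss, because a day 1 value may exist and section 9.1 fixes no time point. That stands.

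A reader might also infer that every intraoperative conversion counts as removal and is lost. The documents do not support this. Section 5.2.2 permits conversion, and sections 6.2 and 9.1 count open or radical conversion among the outcomes. Conversion is not part of this point. Nor is the absence of a named analysis population in section 9.3, which is a separate omission and would exist whatever 5.6 said.

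**Conclusion.** The point holds in a limited form. As written, 5.6 ends study participation when a trigger is met, and 5.5 does not restore the renal measurements. For a randomised patient removed after surgery and before month 3, the loss of postoperative SRF is firm, and the loss of eGFR after day 1 is possible.

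Each such patient costs 2.5% of an arm's SRF data, taking the planned 40 per arm. The number is probably small. It might be tempting to conclude that the trial is biased towards the off-clamp technique. The documents do not support that: they give no removal rate, no split of removals by arm and no renal outcome for removed patients. It would also go too far to say that the 3-month tests will not be done. The gap is that the study is not required to record them.

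The conclusion rests on reading removal from the study in its ordinary sense, as the end of study data collection apart from the adverse-event follow-up in 5.5.

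**What to change.** Change data collection and reporting only. No change to clinical management or to conversion decisions is proposed.

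- Reword 5.6, and align 5.5, so that stopping the intervention or having an adverse event does not by itself end data collection. Only withdrawal of consent for follow-up should do that.
- For every randomised patient who has not withdrawn that consent, record the 3-month creatinine/eGFR and renal scan results obtained in standard care, and the annual results where they apply. This means retrieving existing results. It does not require a scan that routine care would not have included.
- Keep these patients in their assigned arm for the renal-function comparison.
- Report removals by arm, with reason and timing. Section 5.6 already requires the reason on the case report form, so only timing and the tally are new.

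The cost is a few sentences and a little more data retrieval. The tests are already described as standard of care (5.4), and a 3-month follow-up form already exists (7.0).
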